1.2 Prior Experience (if applicable)

Drs. [name], [name], and [name] have extensive experience using electronic medical record data to identify patients with chronic pain.^{8,10-20} Drs. [name] and [name] have experience conducting hospital-based intervention studies including those focused on transitions of care.²¹⁻²⁹ YNHH currently has an opioid stewardship program, chaired by [name] with [name] as a member, that employs system-based opioid surveillance such as a dashboard to identify patients receiving opioids, automatic “best practice” prompts in the electronic medical record to avoid opioid prescribing when opioids have not been used in the previous 24 hours, and automatic “best practice” prompts to prescribe naloxone at discharge for patients who are prescribed opioids greater than a certain dose. The study proposed will leverage existing YNHH clinical pharmacy staff and opioid stewardship resources. [name] has also developed landmark hospital-based Addiction Medicine Consult Programs and developed nationally recognized pain and OUD treatment education for clinicians.³⁰⁻³⁴ [name] has led innovations to address hospital opioid prescribing.³⁵ **Relevance:** The investigators have experience using electronic medical records to identify patients with chronic pain and OUD and in conducting hospital-based intervention studies. The proposed work will evaluate the feasibility and efficacy of an enhanced version of an existing opioid stewardship program to meet the needs of hospitalized patients with chronic pain and opioid misuse. **Rationale/Significance**

1.3 Rationale and Study Significance

Hospitalizations of patients with CP and opioid dependence are increasing nationally³ and are an important opportunity to optimize the use of medications for CP and OUD, when indicated. Hospitalizations can also be risky for this patient population, as opioids are the second most common cause of preventable adverse events in hospitalized patients.⁴ For example, administration of opioids and other controlled substances such as benzodiazepines can contribute to new episodes of or higher dosages of long-term opioids after hospital discharge. Additionally, there has been increased recognition of the “stress of hospitalization,” including sleep deprivation, immobility, and uncertainty about care plans.⁵ This stress may exacerbate CP, anxiety and depression. Our work has demonstrated that generalist prescribers rarely follow opioid prescribing guidelines⁶⁻⁸ and most prescribing decisions regarding CP and opioid dependence during hospitalization are made by clinicians with limiting training in the management of these conditions. As a result, front-line hospital prescribers often do not prescribe opioids and other controlled substances according to best practices for patients with CP and opioid dependence, with or without OUD. While addiction consult services are growing, they are not always involved in the care of patients with CP, and are limited to a small number of academic medical centers.

There are a range of key decisions regarding hospitalized patients with CP and opioid dependence that clinicians face. For instance, the management of methadone, buprenorphine and naltrexone for patients with OUD involves clinical considerations including important patient preferences. Additionally, tailored treatment may be necessary for hospitalized patients with CP and opioid dependence who experience both acute pain from injury, surgery or medical procedures as well as exacerbations of CP during hospitalization. Clinical decisions about which medication and non-medication-based pain treatments to deploy involve weighing risks and benefits, including the impact of treatments on OUD and comorbid anxiety and depression. These decisions, especially those related to medications, may have important consequences with respect to CP, as well as opioid dependence with or without OUD, anxiety, depression and health care utilization.

Interventions that maximize benefits and minimize risks of opioid prescribing for hospitalized patients with CP and opioid dependence are critically needed as this becomes an increasingly common clinical scenario. Currently, the YNHHS Opioid Stewardship Program, modelled after “antibiotic stewardship” programs that manage the adverse individual and public health effects of antibiotic prescribing, aims to improve opioid prescribing in the hospital setting however has limited impact on the care of individual patients as the only patient-specific intervention implemented is the delivery of automated “best practice alerts” (i.e., “pop-ups”) through the electronic medical record. The proposed study intervention will build on to current Opioid Stewardship Program by including real-time interaction and guidance from an addiction medicine and pain-trained physician/pharmacist team, focusing on implementing and tailoring best practices for use of opioids for patients hospitalized with CP and opioid dependence.

1.4 Purpose of Study/Potential Impact

The purpose of this work is to investigate the feasibility and preliminary efficacy of an enhanced opioid stewardship program, tailored to the needs of hospitalized patients with chronic pain with opioid dependence, incorporating real-time guidance from an addiction medicine and pain-trained physician/pharmacist team, using a pilot randomized clinical trial format. Findings from this research may improve pain management and decrease risk of opioid-related adverse events among patients with chronic pain.

1.5 Potential Risks and Benefits

1.5.1 Potential Risks

Opioid Stewardship Intervention: The goal of the enhanced opioid stewardship intervention is to manage chronic pain while reducing risk of inappropriate/risky opioid use and preventing harms of opioid use. We anticipate no significant adverse effects from participating in the opioid stewardship intervention. It is important to note that the intervention team will not have a direct impact on patient care; all guidance related to appropriate pain management and adjuvant therapies will be provided to a participant’s clinical team, who will be ultimately responsible to decide whether to apply such guidance to their patient’s care. Nonetheless, there is a small chance that efforts to manage pain in the context of best practices for opioid use may inadvertently and temporarily result in distress in

participants. Distress may include temporary increases in pain or physical or mental discomfort from opioid withdrawal symptoms. All patients will receive best practice treatment for their withdrawal symptoms and treatment of OUD, if present, as part of usual clinical care.

Rating scales and questionnaires: Rating scales and questionnaires are all non-invasive, however, some questions may be distressing to participants.

Confidentiality: There is a small risk of a breach of data or private information associated with participation in this study.

1.5.2 Potential Benefits

Participants in this pilot RCT may potentially derive certain benefits, although none are guaranteed. Immediate potential benefits include improved pain management, including decreased severity or frequency of pain, and reduced interference from pain in going about daily activities. Another immediate potential benefit would be reduced risk of opioid-related adverse events during hospitalization, including over-sedation, gastrointestinal side effects, as well as identification of an opioid use disorder, leading to treatment consistent with usual care (which would be recommended by the intervention team). Potential long-term benefits include decreased risk of developing OUD or improved treatment of an existing OUD, and better pain management and quality of life. These benefits would apply primarily to the intervention group. The control group will be treated with usual hospital-based care.

2 Study Purpose and Objectives

2.1 Hypothesis

Participants randomized to the intervention will have less pain, fewer opioid-related adverse events, and greater improvement in quality of life compared with control participants, as measured at hospital discharge.

The care of intervention participants will also include a greater number of guideline-based care elements for opioid stewardship compared with the care of control participants, as measured at hospital discharge.

2.2 Primary Objective

The primary objective of this study is to determine whether an enhanced opioid stewardship program, tailored to the needs of patients with chronic pain, is feasible to implement in a hospital setting. Feasibility will be measured using standard metrics and are described in Section 3.2.1.

2.3 Secondary Objective (if applicable)

There are two secondary objectives to this pilot RCT, both related to efficacy.

One secondary objective is to determine whether an enhanced opioid stewardship program increases use of guideline-based opioid care. The other secondary objective of this study is to determine whether an enhanced opioid stewardship program reduces pain frequency, intensity, and interference and decreases the risk for opioid-related adverse events among

adult patients with chronic pain hospitalized on medical units at Yale-New Haven Hospital, York Street and Saint Raphael campuses. Outcomes for the secondary objectives are described in section 3.2.2.

3 Study Design

3.1.1 General Design Description

We propose a pilot randomized controlled trial of 100 adult patients hospitalized on medicine units at Yale-New Haven Hospital York Street Campus and Saint Raphael campus. The trial will be prospective and focus primarily on feasibility.

3.1.2 Study Date Range and Duration

The study will commence upon approval of this IRB application (expected April 2022) and will finish upon completion of all study activities for 100 enrolled participants. The expected duration of participation by a given participant will be from the day of enrollment to 30 days after discharge from the admission during which they were enrolled.

3.1.3 Number of Study Sites

There will be one study site- Yale-New Haven Hospital, SRC and YSC campuses.

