The Yale-New Haven Hospital System has implemented an opioid stewardship program, modelled after “antibiotic stewardship” programs that manage the adverse

individual and public health effects of antibiotic prescribing, to improve opioid prescribing in the hospital setting.⁴ This program, endorsed by the Joint Commission, brings focused expertise to promote the appropriate use of opioids and improve patient outcomes through opioid use monitoring and development of “best practice” recommendations regarding opioid prescribing. However, the YNHHS Opioid Stewardship Program has limited impact on the care of individual patients, as the only patient-specific intervention implemented is the delivery of automated “best practice alerts” (i.e., “pop-ups”) through the electronic medical record of clinicians.

The purpose of the proposed study is to evaluate the feasibility and preliminary efficacy of an opioid stewardship program that provides real-time interaction and guidance from an addiction medicine and pain-trained physician/pharmacist team, focusing on implementing and tailoring best practices for use of opioids for patients hospitalized with CP and opioid dependence. We propose to evaluate the implementation and assess preliminary efficacy of the intervention.

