3.2 Outcome Variables

3.2.1 Primary Outcome Variables

The primary outcomes for this pilot RCT will relate to feasibility of recruitment and retention. For recruitment, we will describe the number of patients screened vs. the number of patients eligible; the number of patients eligible vs. the number enrolled; and the hospital day of enrollment (in relation to the admission and discharge dates). For retention, we will describe the number of participants in the intervention group for whom we are able to deliver the full enhanced opioid stewardship intervention, as well as the number in intervention and control groups who complete the peri-discharge evaluation.

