3.3.1 Number of Participants

We anticipate 10-50 records will be returned in the Epic report each day that will be screened for eligibility. We aim to recruit 100 participants who meet all inclusion and exclusion criteria for the trial, for a total of approximately 50 each in the intervention and control arms. Screening and enrollment will continue until the target sample size has been reached, with a goal of recruiting 5-10 patients per week.

Eligibility Criteria/Vulnerable Populations

In order to be eligible for inclusion in the study, an individual must meet all of the following criteria:

- adults (age ≥ 18 years);
- admitted at YNHH (YS and SRC) on medical units;
- identified as having chronic pain and prescribed opioids.
- Have opioid dependence (evidenced by ongoing opioid prescription, meeting DSM-5 criteria for OUD, or clinical history)

Any individual who meets any of the following criteria will be excluded from participation in this study:

- active cancer
- current pregnancy
- hospice care/comfort measures only
- admission to inpatient psychiatry
- completed or planned Addiction Medicine consult during hospitalization

4. Study Methods/Procedures

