3.4 Study Procedures

All patients will receive standard hospital care. Patients who are identified as eligible for the study via screening in Epic will be approached during hospitalization, undergo informed consent, and be enrolled in the study. Those who consent will be asked questionnaires

related to patient reported outcomes of pain, anxiety, depression and quality of life at baseline. Patients will then be randomized on a 1:1 ratio to either the enhanced opioid stewardship program arm or a control (i.e., usual care) arm. Patients who are randomized to the intervention arm will have their medical record reviewed by both a pharmacist and a physician trained in pain and addiction medicine. The pharmacist and physician will provide best practice guidance via an Epic note to the primary care teams to consider, versus continuation with their usual care plan. All guidance will be voluntary for clinical teams to follow. All participants will be tracked daily in Epic for discharge status, and when discharge within 48 hours is anticipated, the study team will perform the final patient interview, which will be very similar to the baseline interview and composed of questionnaires related to pain, anxiety, depression, and quality of life. Medical record abstraction will be performed to abstract relevant characteristics of each participant's hospitalization, use of guideline-based best practices for pain management and opioid stewardship at discharge, and incidence of readmissions and ED visits within 30 days after discharge for the hospitalization during which the participant was recruited.

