3.5 Study Schedule

The total number of visits as part of this intervention will include (1) screening and consent, (2) baseline interview (may be combined with consent visit, per participant's preference), and (3) a peri-discharge interview (within 48 hours of anticipated discharge). The total number of study visits is expected to be three per participant, with the potential for greater frequency of interaction via phone. Each visit will last approximately 30 minutes or less.

Study Schedule:

Study Activity	Time frame/duration
1. Currently hospitalized patients screened in Epic	Every weekday
2. Eligible participants approached by study team	Every weekday
3. Study described, questions answered, written informed consent obtained	30 minutes
4. Participant completes baseline interview; \$25 gift card provided	15 minutes
5. Participant randomized to intervention or usual care arm	1 minute
6. Participant's hospitalization tracked for anticipated discharge status	Daily
7. Intervention participants' charts reviewed by study team's addiction medicine physician/pharmacist for adherence to best practice guidelines for pain management/opioid stewardship.	Once, within 24 hours of randomization
8. Study addiction medicine physician composes note in intervention participant's medical record with recommendations to optimize guideline-based pain management/opioid stewardship	Once
9. Study addiction medicine physician alerts primary clinical care team via Mobile Heart Beat of Epic note regarding guideline-based care recommendations	Once
10. Final participant interview performed within 48 hours of anticipated discharge; \$25 gift card provided	15 minutes
11. Medical record abstraction performed for hospitalization characteristics, use of guideline-based best practices for pain management/opioid stewardship, and readmissions/ED visits within 30 days	1-30 days post-discharge

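### Minor, low-cost improvement: specify allocation stratified by the two campuses and pre-specify campus as a term in the between-arm comparisons

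*Combined protocol and SAP*

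**What the plan says.** Section 3.1.3 of the protocol says "There will be one study site- Yale-New Haven Hospital, SRC and YSC campuses". Sections 3.1.1 and 3.3.1 set the sample at 100 patients from medical units on these campuses, "for a total of approximately 50 each in the intervention and control arms".

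On allocation, Section 3.4 says "Patients will then be randomized on a 1:1 ratio to either the enhanced opioid stewardship program arm or a control (i.e., usual care) arm", and row 5 of the schedule in Section 3.5 says only "Participant randomized to intervention or usual care arm". The protocol does not describe sequence generation, blocking, stratification or concealment.

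On the comparator, Section 1.5.2 says "The control group will be treated with usual hospital-based care". The first secondary outcome in Section 3.2.2 is a count of care elements, most of them clinicians' orders, abstracted from the record.

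On analysis, Sections 3.7.1 and 3.7.3 plan mainly bivariate tests, used both to check covariate balance and to compare arms. Multivariable regression is exploratory and optional, chiefly for the case where imbalance turns up. Campus is not named as a covariate. Section 3.7.2 gives no power calculation.

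The primary outcomes are not between-arm effects: "The primary outcomes for this pilot RCT will relate to feasibility of recruitment and retention" (Section 3.2.1).

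**The concern.** Campus is known for every patient before randomisation. The care-element count depends on what treating teams order, and under Section 3.4 those teams are free to follow the guidance or not. It is plausible that ordering practice differs between campuses, in which case campus predicts the outcome. With about 50 per arm, the two arms can by chance hold noticeably different campus mixes, and an unadjusted comparison would carry that difference.

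The plan's safeguard is to look for imbalance afterwards and then perhaps adjust. That leaves the choice of model dependent on the data. Stratifying the allocation, or fixing campus as a model term in advance, avoids this. What is at stake is the reading of the secondary contrasts in a single trial and a little of their precision. The primary feasibility results are not at stake.

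**Working it through.** **Inputs from the protocol.** N = 100 (3.1.1), about 50 per arm (3.3.1), 1:1 (3.4), two campuses (3.1.3). There is no power calculation to reproduce; 100 at 1:1 is 50 + 50.

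**Assumptions, because the protocol gives no figures.** The smaller campus supplies K = 10 to 50 of the 100 patients. The campus difference in mean outcome is g = 0.25, 0.5 or 0.8 within-campus SDs.

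**Step 1: chance imbalance in campus share, arms fixed at 50/50.** Let X be the number of smaller-campus patients in one arm. X is hypergeometric (100 patients, K from that campus, 50 drawn). The difference in campus share is D = |X − (K − X)|/50 = |2X − K|/50. For even K it moves in steps of 4 points, so 10 points or more means 12 or more in practice.

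| Smaller-campus share | P(D ≥ 10 points) | P(D ≥ 20 points) |
|---|---|---|
| 50% | 31.7% | 7.1% |
| 40% | 30.7% | 6.6% |
| 30% | 27.5% | 4.9% |
| 20% | 21.1% | 2.3% |
| 10% | 9.2% | 0.1% |

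A difference of 30 points or more has probability 0.3% or less. If allocation were instead simple 1:1 (simulation of 400,000 trials), the figures for at least 10 points would be 36.8%, 28.7% and 10.4% at smaller-campus shares of 50%, 30% and 10%. For at least 20 points they would be 5.7%, 3.1% and under 0.1%. The order of size does not depend on which scheme is assumed.

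**Step 2: shift in the arm difference.** Shift = g × D. The standard error of the arm difference, in within-campus SDs, is √(2/50) = 0.20.

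- g = 0.5, D = 0.10: 0.05 SD; 0.05/0.20 = 0.25 SE.
- g = 0.5, D = 0.20: 0.10 SD; 0.50 SE.
- g = 0.8, D = 0.10: 0.08 SD; 0.40 SE.
- g = 0.8, D = 0.20: 0.16 SD; 0.80 SE.

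For g = 0.5 the shift reaches half an SE only at D ≥ 20 points, at most 7.1% of randomisations. For g = 0.8 it needs D ≥ 0.10/0.8 = 12.5 points, which in 4-point steps means 16 or more: 16.1% at an even campus split.

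**Step 3: error rate of the unadjusted two-sided 5% test, even campus split.** The test's own standard error uses the total SD, s = √(1 + g²/4). Given imbalance D, the rejection rate under no effect is 1 − Φ(1.96s − gD/0.20) + Φ(−1.96s − gD/0.20). At D = 0.20:

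- g = 0.25: 5.5%.
- g = 0.5: s = 1.031, so 1 − Φ(2.020 − 0.5) + Φ(−2.020 − 0.5) = 7.0%.
- g = 0.8: 9.7%.

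At D = 0.10 it is about 5% for all three. Averaged over all randomisations (simulated for g = 0.5 and 0.8) it is about 4.7%, so the unadjusted test is not inflated overall.

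**Step 4: gain from using campus.** At an even campus split, the outcome variance within arm falls from 1 + g²/4 to 1. For g = 0.5 that is 1.06 to 1.00, a standard error about 3% smaller (√1.0625 = 1.031). For g = 0.8 it is 1.16 to 1.00, about 7% smaller (1/√1.16 = 0.928). N stays at 100.

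**The case against.** The strongest case against is that randomisation already deals with this. The estimate is unbiased over randomisations, ordinary standard errors allow for chance imbalance, and the overall error rate stays at about 5%. All of that stands. What remains is a shift conditional on the imbalance that actually occurs, and a modest loss of precision.

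Nor does the protocol show that usual care differs by campus. Section 1.1 describes the background program at system level ("The Yale-New Haven Hospital System has implemented an opioid stewardship program"), and Section 3.6.1 describes one Epic report covering both campuses. If ordering habits vary, unit or clinical team may matter as much as campus. This also stands: campus is a plausible predictor, not a documented one. The system-wide program does not prove uniform ordering either, since Sections 1.1 and 1.3 say its only patient-specific element is automated alerts.

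The trial is a pilot, its between-arm comparisons are exploratory, and adjusted regression is already foreseen. That limits the importance of the point but does not remove the case for a nearly costless change.

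Some stronger readings are tempting and are not supported:

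- A reader might infer that the plan states an unstratified or unblocked scheme. It is silent on the method. Even simple allocation, with a 36.8% chance of a 55/45 or worse split, could fit the stated target of approximately equal arms.
- A reader might infer that campus confounds the feasibility results. Those are descriptive counts.
- A reader might infer that stratification is needed for a feasibility reading by campus. Screening, eligibility, enrolment and day of enrolment all precede randomisation, and delivery and completion can be tabulated by campus under any scheme.
- A reader might infer that REDCap makes stratification free. Section 3.4.1 describes it for data collection and management, and no randomisation module is mentioned.

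**Conclusion.** The point holds as a minor improvement. Two campuses are pooled as one site, the allocation method beyond 1:1 is not described, and campus is not pre-specified in any comparison. If campus predicts ordering practice, there is a 9% to 32% chance of a campus-share difference of at least 10 points and a 0.1% to 7% chance of at least 20 points, for a smaller-campus share of 10% to 50%. The resulting shift in a secondary contrast is usually under half a standard error.

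This rests on assumed campus shares and assumed campus differences of up to 0.8 SD; the protocol gives neither. The shift cannot be put in numbers of care elements, because no SD and no campus difference for the count is stated. The conclusion does not extend to bias on average or to the primary outcomes.

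**What to change.** 1. In Section 3.4 and row 5 of the Section 3.5 schedule, state that allocation is concealed and uses randomly varying permuted blocks stratified by campus (YSC, SRC). The protocol already places randomisation after consent and the baseline interview, so that order need not change.
2. In Section 3.7.3, pre-specify campus as a term in the between-arm comparisons whatever balance is observed, in place of adjustment triggered by imbalance.
3. Optionally, tabulate the Section 3.2.1 counts by campus. This does not depend on stratification.

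The cost is a small set-up task for a two-stratum list, a sentence or two of protocol text, and one degree of freedom (98 to 97 residual in a linear model with 100 patients). Incomplete final blocks can leave the arms slightly unequal. With blocks of at most 6, for illustration, the excess is at most 3 per campus, so 53/47 at worst. No extra patients or visits are needed.
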